## 10. Secondary analyses

The subsequent secondary analyses will be adjusted using the following baseline covariates: age, weight, bone marrow transplantation and PIM2 score. The baseline covariates have been selected *a priori* for their anticipated strong association with the outcome. No further selection of covariates will be performed based on imbalance at baseline or significance in univariable analyses.

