#### and

3) either acute respiratory failure or acute on chronic respiratory failure as defined below.

Acute respiratory failure is defined as a new onset of hypoxaemia, tachypnoea and chest x-ray changes developing in the previous 48 hours. All of the following age specific criteria must be met:

i.hypoxaemia: arterial oxygen saturation (SpO2) less than 90% in room air

and

ii.tachypnoea: respiratory rate greater than approximate 90th centile for age: 55 (<12 months); 45 (12 months – <2 years); 30 (≥2 years – <4 years); 25 (≥4 years – <10 years) and 20 (≥10 years – <18 years)

[unless the child is receiving a continuous infusion of an opiate at any dose, in which case the tachypnoea criteria do not apply]

and

iii. *chest X-ray changes*: radiological evidence of acute pulmonary infiltrates developing in the previous 48 hours.

Acute on chronic respiratory failure is defined as a significant acute deterioration, in the previous 48 hours, in infants and children with pre-existing chronic lung disease

requiring long-term supplemental oxygen therapy. All of the following age-specific criteria must be met:

i. *hypoxaemia*:  $SpO_2$  less than 90% in room air and a requirement for increased supplemental oxygen by  $\geq$ 30% of baseline flow rate (or  $\geq$ 30% increase from baseline fraction of inspired oxygen (FiO2)where measured).

and

ii. tachypnoea: increased respiratory rate >20% above baseline and greater than approximate  $90^{th}$  centile for age: 55 (<12 months); 45 (12 months – <2 years); 30 ( $\geq$ 2 years – <4 years); 25 ( $\geq$ 4 years – <10 years) and 20 ( $\geq$ 10 years – <18 years)

[unless the child is receiving a continuous infusion of an opiate at any dose, in which case the tachypnoea criteria do not apply]

and

iii. *new chest X-ray changes:* radiological evidence of acute pulmonary infiltrates developing in the previous 48 hours.

[The cause of acute or acute on chronic respiratory failure is not a consideration. This is a pragmatic trial to assess the response of the clinical syndrome of acute respiratory failure to two different management strategies. Acute respiratory failure might arise from an acute lower respiratory tract infection, systemic sepsis or inflammatory processes, such as veno-occlusive disease, or graft vs. host disease with varying degrees of fluid retention/overload.]

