### **3.3.2 Secondary**

The secondary outcome measures are:

- maximum and aggregate paediatric logistic organ dysfunction score (PELOD) at 30 days post-randomisation;
- mortality at 30 days post-randomisation;
- requirement for Level 2 or Level 3 respiratory support within 30 days post-randomisation;
- days free from any ventilator support (Level 2, 3 or 4 respiratory support) at 30 days post-randomisation;

- days free from supplemental oxygen (i.e. above pre-acute respiratory failure requirement) at 30 days post-randomisation;
- hospital mortality;
- mortality at 90 days post-randomisation; and
- mortality at one year post-randomisation.

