### **8.2 Baseline characteristics**

The following baseline (pre-randomisation) demographic and clinical factors will be summarised by treatment group but not subjected to statistical testing:

- Age group (<12 months; ≥12 months)
- Age in months
- Gender
- Weight
- Acute respiratory failure or acute on chronic respiratory failure
- Bone marrow transplant
- Cause(s) of impaired immunity
- Suspected cause of acute respiratory failure (at the time of randomisation)
- PIM2r score
- Supplemental O2 requirement (pre-acute respiratory failure)

Numbers and percentages within each treatment group will be reported for categorical factors; means (with SD) and medians (with IQR) within each treatment group will be reported for continuous factors. P values will not be calculated or quoted.

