## 9. Primary analysis

The number and percentage of patients requiring invasive mechanical ventilation 30 days following randomisation will be reported. Invasive mechanical ventilation by 30 days following randomisation will be compared between the treatment groups, unadjusted, using Fisher's exact test and reported as a relative risk with 95% confidence interval and as an absolute risk reduction with 95% confidence interval.

As a secondary analysis, the primary outcome will also be analysed using logistic regression adjusted for the following baseline covariates: age, weight, bone marrow transplantation and PIM2 score. Other covariates originally planned for inclusion in the adjusted analysis (cause of impaired immunity, suspected main cause of acute respiratory failure) will not be included in the model due to the smaller sample size. The results of the logistic regression model will be reported as an adjusted odds ratio with a 95% confidence interval. The unadjusted odds ratio will be presented for comparison.

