### **10.5 Days free from supplemental oxygen at 30 days post-randomisation**

The mean number of days free from any supplemental oxygen ventilator support up to 30 days following randomisation, within each treatment group will be reported. Patients that die within 30 days post-randomisation will be considered to have zero days free from supplemental oxygen. Differences between the treatment groups will be compared using multilevel linear regression - adjusted for the same *a priori* baseline variables reported above. The results of the multilevel linear regression model will be reported adjusted, and unadjusted for comparison, with 95% confidence interval for the coefficients.

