ix. Table 5e: Logistic regression model for requirement for Level 2 or Level 3 respiratory support within 30 days post-randomisation

Variables	Odds ratio	95% CI	P-value
Treatment			
Usual treatment	1		
Early CPAP	X.XX	X.XX, X.XX	0.XXX
Age (per year)	X.XX	X.XX, X.XX	0.XXX
Weight (per 5kg)	X.XX	X.XX, X.XX	0.XXX
Bone marrow transplantation			
No	1		
Yes	X.XX	X.XX, X.XX	0.XXX
PIM2r score (per point)	X.XX	X.XX, X.XX	0.XXX

x. Table 5f: Linear regression model for days free from any ventilator support at 30 days post-randomisation

Variables	Coefficient	95% CI	P-value
Constant	X.XX	X.XX, X.XX	0.XXX
Treatment			
Usual treatment	0		
Early CPAP	X.XX	X.XX, X.XX	0.XXX
Age (per year)	X.XX	X.XX, X.XX	0.XXX
Weight (per 5kg)	X.XX	X.XX, X.XX	0.XXX
Bone marrow transplantation			
No	0		
Yes	X.XX	X.XX, X.XX	0.XXX
PIM2r score (per point)	X.XX	X.XX, X.XX	0.XXX

- xi. Table 5g: Linear regression model for days free from supplemental oxygen at 30 days post-randomisation

Variables	Coefficient	95% CI	P-value
Constant	X.XX	X.XX, X.XX	0.XXX
Treatment			
Usual treatment	0		
Early CPAP	X.XX	X.XX, X.XX	0.XXX
Age (per year)	X.XX	X.XX, X.XX	0.XXX
Weight (per 5kg)	X.XX	X.XX, X.XX	0.XXX
Bone marrow transplantation			
No	0		
Yes	X.XX	X.XX, X.XX	0.XXX
PIM2r score (per point)	X.XX	X.XX, X.XX	0.XXX

- xii. Table 5h: Logistic regression model for hospital mortality

Variables	Odds ratio	95% CI	P-value
Treatment			
Usual treatment	1		
Early CPAP	X.XX	X.XX, X.XX	0.XXX
Age (per year)	X.XX	X.XX, X.XX	0.XXX
Weight (per 5kg)	X.XX	X.XX, X.XX	0.XXX
Bone marrow transplantation			
No	1		
Yes	X.XX	X.XX, X.XX	0.XXX
PIM2r score (per point)	X.XX	X.XX, X.XX	0.XXX

- xiii. Table 5i: Logistic regression model for mortality at 90 days post-randomisation

Variables	Odds ratio	95% CI	P-value
Treatment			
Usual treatment	1		
Early CPAP	X.XX	X.XX, X.XX	0.XXX
Age (per year)	X.XX	X.XX, X.XX	0.XXX
Weight (per 5kg)	X.XX	X.XX, X.XX	0.XXX
Bone marrow transplantation			
No	1		
Yes	X.XX	X.XX, X.XX	0.XXX
PIM2r score (per point)	X.XX	X.XX, X.XX	0.XXX

[figure not shown]
xiv. Table 5j: Logistic regression model for mortality at one year post-randomisation

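### The adjusted model for oxygen-free days omits the pre-illness oxygen requirement that the outcome is measured against; adding it is a cheap improvement of uncertain gain

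*SAP*

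**What the plan says.** SAP 3.3.2 (and Protocol 5.2) defines the outcome as "days free from supplemental oxygen (i.e. above pre-acute respiratory failure requirement) at 30 days post-randomisation". Each child is scored against his or her own level before the acute illness.

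Protocol 6.1 admits children with that kind of requirement under a separate definition. Acute on chronic respiratory failure applies to those with chronic lung disease "requiring long-term supplemental oxygen therapy", with its own hypoxaemia and tachypnoea criteria.

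SAP 8.2 lists the pre-illness oxygen requirement among the baseline characteristics, and dummy Table 1 shows it as No/Yes.

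SAP 10 fixes the covariates for every secondary model: "The subsequent secondary analyses will be adjusted using the following baseline covariates: age, weight, bone marrow transplantation and PIM2 score". It rules out later selection on imbalance or significance. Table 5g, titled "Linear regression model for days free from supplemental oxygen at 30 days post-randomisation", has rows for treatment and those four covariates only. Minimisation uses age group and bone marrow transplantation (Protocol 9.0).

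SAP 10.5 words the outcome differently: "The mean number of days free from any supplemental oxygen ventilator support up to 30 days following randomisation". It calls the model multilevel and names no level. Deaths within 30 days score zero.

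**The concern.** SAP 10 says its covariates were chosen because they were expected to be strongly associated with the outcome, yet one list serves every outcome. For oxygen-free days, the pre-illness requirement is an obvious candidate by that criterion. It sets the level a child must return to, and it marks children with chronic lung disease, who may recover at a different pace. No covariate in the model is specified to capture chronic lung disease; the protocol's chronic diagnosis term (Protocol 19.2) is not among the SAP's four.

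The reason for shortening the list, given in SAP 9, is the smaller sample. It is stated for the logistic model of intubation, where the number of events limits the number of terms. It weighs less for a linear model to which every child contributes a value.

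Two things are at stake for this one outcome. The confidence interval may be wider than it need be. And if Table 1 shows more long-term-oxygen children in one arm, SAP 10 leaves no route to adjust for it, because covariates may not be added in response to imbalance.

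**Working it through.** **Inputs from the documents.** The planned size is 148, 74 per group (SAP 4). It reproduces: for 35% v 14%, 80% power and two-sided 5%, the pooled-variance formula gives 65 per group, and the continuity correction raises this to 74. That figure concerns intubation. It matters here only because the interim analysis at 50% recruitment could not be held for lack of patients (SAP 12), which puts the actual number below 74. I use 73 as the upper limit and 40 as an illustration. The actual number is not stated, and the SAP gives no precision figure for oxygen-free days.

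**Inputs not in the documents.** The outcome SD, the share of children on home oxygen, and the association of home oxygen with the outcome are all assumptions below.

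**1. Gain or loss from one extra term.** Let R be the partial R-squared of the requirement, given treatment and the four existing covariates. Approximately,

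SE ratio (with / without) = sqrt[(1 - R) x (1 + 1/(N - 9))].

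| R | N = 73 | N = 40 |
|---|---|---|
| 0 | 1.008 | 1.016 |
| 0.02 | 0.998 | 1.006 |
| 0.05 | 0.982 | 0.990 |
| 0.10 | 0.956 | 0.964 |
| 0.20 | 0.901 | 0.909 |

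Setting the ratio to 1 gives a break-even R of 1/(N - 8): 1/65 = 1.5% at N = 73 and 1/32 = 3.1% at N = 40.

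**2. Simulation check.** The setting was a null treatment effect, four unrelated covariates, residual SD 10 days, 10% or 30% on home oxygen, and an effect of home oxygen from 0 to 10 days. At N = 40 the empirical SE ratio ran from 1.018 to 0.932. Both estimators stayed within 0.2 days of the true null, so the omission causes no bias.

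**3. An assumed middle case.** Take 37 v 36 children, SD 11 days, 20% on home oxygen and an 8-day difference between those with and without it.
- Share of variance: 0.2 x 0.8 x 8^2 / 11^2 = 10.24 / 121 = 8.5%.
- Simulated SE: 2.58 without the term and 2.49 with it, a ratio of 0.965, or about 3.5% narrower.
- This compares an unadjusted difference with one adjusted for home oxygen alone. Overlap with age, weight, transplantation or PIM2 would shrink the gain.

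**4. Chance imbalance in the same case.**
- SD of the difference in shares: sqrt[0.2 x 0.8 x (1/36 + 1/37)] = 0.094.
- Shift from a 1.96-SD imbalance: 1.96 x 0.094 x 8 = 1.5 days.
- Half-width of the 95% interval: 1.96 x 2.58 = 5.1 days.
- With 10% on home oxygen and 6 days, the shift is 0.8 days; with 30% and 12 days, it is 2.5 days.

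**5. The wording in SAP 10.5.** Read literally, with no reference to the pre-illness level, a child on continuous home oxygen would score about zero throughout. If the other children averaged 15 days (assumption) and 20% were on home oxygen, a 1.96-SD imbalance would move the difference by 1.96 x 0.094 x 15 = 2.75 days. The value of the covariate therefore depends on which wording is applied.

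**The case against.** The strongest reply is that the covariate list is a deliberate choice: one set fixed in advance for all secondary outcomes, shortened because recruitment fell short. Pre-illness oxygen is in neither the protocol's list of data for risk adjustment (11.3) nor its covariates (19.2). The SAP is dated September 2016, after the planned end of recruitment in an open trial, so a late addition needs a reason. All of this is fair, and it is why the point is an improvement and not an error.

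A reader might also draw stronger conclusions that the documents do not support:

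- *That the requirement is the baseline value of the outcome.* It is a chronic yes/no status, whereas the outcome is a count of days. Scoring each child against his or her own prior level already removes part of the dependence. What may remain is a different pace of recovery with chronic lung disease, and deaths scored as zero.
- *That precision is certainly lost.* That depends on an association the documents do not give. If there is none, the extra term costs a little precision.
- *That chance imbalance distorts the result.* Under randomisation the estimate without this covariate has no expected bias, and its interval already covers such imbalance. The argument for adjusting is conditional on the imbalance that is seen.
- *That weight should make way for the new term.* Weight is a protocol covariate (19.2), and nothing shows that it predicts less well.
- *That the other adjusted models need the term too.* Only oxygen-free days are defined by it.

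**Conclusion.** The omission is real and confined to one secondary outcome. Oxygen-free days are measured against a baseline quantity that the SAP tabulates and then leaves out of both the model and the minimisation. The result is a possible loss of precision and no planned way to adjust for an observed imbalance. Validity is not affected.

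The trade is small but favourable if the variable is even modestly prognostic: a bounded cost of about 1-2% of the standard error against a gain of a few per cent, and 9-10% only if the partial R-squared is as high as 0.20. At fewer than 40 children the break-even would be higher. These figures rest on an assumed SD, home-oxygen share and association. Severity is low.

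The inconsistent wording in SAP 10.5 is firmer, because it needs no assumption. It omits the pre-illness reference in SAP 3.3.2, and its multilevel model is not the one in Table 5g.

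**What to change.** Before the outcome data are analysed:

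1. In SAP 10.5 and Table 5g, add the pre-acute supplemental oxygen requirement (yes/no) as one further covariate. Keep age, weight, bone marrow transplantation and PIM2. State that the addition applies to this outcome only, and why.
2. Reconcile the outcome wording in SAP 10.5 with the definition in SAP 3.3.2, so that it is clear whether days are counted against the pre-illness requirement.
3. Reconcile the multilevel model in SAP 10.5 with the linear model in Table 5g; if a multilevel model is meant, name the level.

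If outcome data have already been examined, report the extra adjustment as a post hoc sensitivity analysis and label it so.

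The cost is a few words of text, one table row and one degree of freedom. No new data are needed, since Table 1 already reports the variable.

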### 10.1 Mortality at acute hospital discharge, 30-days, 90-days and one year post-randomisation

The number and percentage of deaths at acute hospital discharge at 30 days, 90 days and one year following randomisation will be reported for the treatment groups. Differences in mortality will be

compared, unadjusted, using Fisher's exact test and relative risk with a 95% confidence interval. They will also be compared adjusted, using logistic regression - adjusted for the same *a priori* baseline variables reported above.

Kaplan Meier curves comparing the treatment groups will be plotted up to 90 days and one year following randomisation.

### **10.2 Requirement for Level 2 or Level 3 respiratory support within 30 days post-randomisation**

The number and percentage of children and infants requiring level 2 or level 3 respiratory support within 30 days following randomisation will be reported for the treatment groups. Differences in requirement of level 2 or level 3 respiratory support will be compared, unadjusted, using Fisher's exact test and relative risk with a 95% confidence interval. They will also be compared adjusted, using logistic regression - adjusted for the same *a priori* baseline variables reported above. The results of the logistic regression model will be reported as an adjusted odds ratio with 95% confidence interval. The unadjusted odds ratio will be presented for comparison.

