## 10.3 Levels of respiratory support

The four levels of respiratory support are as follows:

- Level 1: inspired oxygen therapy on the ward (control group only);
- Level 2: CPAP at 6-10cm H2O;
- Level 3: non-invasive bilevel positive airway pressure (BiPAP) via
  - facemask or helmet;
- Level 4: intubation and mechanical ventilation.

Participants randomised to the intervention group will receive Level 2 respiratory support in the PICU unless their clinical condition changes (see sections 10.4 – 10.6). Participants randomised to the control group will continue to receive Level 1 respiratory support unless their clinical condition changes (see sections 10.4 – 10.6).

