## 10.4 Changes to the level of respiratory support

The following applies to participants in both intervention and control groups:

- participants will progress between the levels in sequence (i.e. Levels 2, 3, 4 in the intervention group and Levels 1, 2, 3, 4, in the control group) unless they stabilise or develop an acute indication for intubation and ventilation (see section 10.6);
- the criteria to escalate from one group to the next or to go directly to intubation and mechanical ventilation are proscribed (see section 10.5);
- decisions to step down respiratory support are at the discretion of the clinical team, aside from a step down from Level 2 to Level 1 for the intervention group, which is not permitted before the end of the 4-day intervention period (unless the participant has progressed to a higher level during this period, in which case they can be stepped down at the discretion of the clinical team).
- the choice of settings *within* each of the four levels are at the discretion of the clinical team.

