### **3.2.1 Intervention group**

Participants allocated to the intervention group (early CPAP) will be admitted to the PICU and receive CPAP of at least 6cm H2O with supplemental oxygen for a minimum of 12 hours per day for at least four consecutive days (Level 2 respiratory support). The interface for delivering CPAP (i.e. via face mask, helmet or infant flow-driver) will be at the discretion of the clinical team responsible for the participant's care. All other care will be determined by the clinical team primarily responsible for the participant's care.

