### **8.3 Clinical management**

Clinical management will be summarised by treatment group but not subjected to statistical testing.

The treatment groups will be compared for the following:

- Admitted to PICU
- Length of stay in PICU
- CPAP (Level 2 respiratory support) received
- Length of stay in acute hospital (from randomisation)

Numbers (%) or means (SD) and medians (IQR), as appropriate, will be given in each treatment group. P values will not be calculated or quoted.

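### The secondary outcome of Level 2 or Level 3 support is met by receiving the allocated CPAP, so its between-arm test does not estimate a treatment effect

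*SAP*

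**What the plan says.** The outcome is listed in Protocol 5.2 and SAP 3.3.2. SAP 10.2 says that the number and percentage of children "requiring level 2 or level 3 respiratory support within 30 days following randomisation will be reported for the treatment groups". It continues: "Differences in requirement of level 2 or level 3 respiratory support will be compared, unadjusted", using Fisher's exact test and a relative risk, followed by a logistic model adjusted for age, weight, bone marrow transplantation and PIM2. Table 4 gives the outcome a row with p values. The model has its own shell, "Table 5e: Logistic regression model for requirement for Level 2 or Level 3 respiratory support within 30 days post-randomisation".

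The same documents define Level 2 as CPAP and make it the allocated treatment:

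- SAP 3.2.1 specifies CPAP "for a minimum of 12 hours per day for at least four consecutive days (Level 2 respiratory support").
- Protocol 10.3: "Participants randomised to the intervention group will receive Level 2 respiratory support in the PICU unless their clinical condition changes".
- Protocol 10.4 makes an exception to clinical discretion: "step down from Level 2 to Level 1 for the intervention group, which is not permitted before the end of the 4-day intervention period". Children who have first moved to a higher level are exempt.
- For the other arm, Protocol 10.3 says: "Participants randomised to the control group will continue to receive Level 1 respiratory support unless their clinical condition changes".

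SAP 8.3 separately lists "CPAP (Level 2 respiratory support) received" as a descriptive item without a p value.

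**The concern.** The same recorded event means different things in the two arms. In the CPAP arm, Level 2 support shows that the protocol was followed. In the control arm, it shows that the child got worse and was escalated. Nothing in SAP 10.2 removes the allocated CPAP from the count.

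A two-sided 5% test of that difference therefore does not address whether early CPAP changes the need for respiratory support. CPAP could halve the need, or have no effect on it, and the CPAP arm would still be expected to show the higher rate. At stake is a named secondary outcome whose row in Table 4 could show roughly double the rate of support in the CPAP arm with a small p value. There is also a model that may not be estimable.

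**Working it through.** **The plan's own figures.** The documents give no figure for this outcome. The only planned size, in Protocol 19.1, is for intubation: 35% vs 14%, 80% power, two-sided 5%. The usual two-proportion formula gives 65 per arm. With the continuity correction it gives 74 per arm, or 148 in total, which matches the plan. It does not bear on the Level 2/3 outcome.

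**Inputs and assumptions.**

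- Control rate of Level 2/3 support, *c*: not given. Range used: 35% to 70%. The low end borrows the planned intubation rate. Protocol 10.4 has children pass through the levels in sequence, so children who stabilise at Level 2 or 3 would push *c* above the intubation rate. Direct intubations under Protocol 10.6 would pull it down.
- Share of CPAP-arm children receiving any Level 2/3 support, *q*: not given. Range used: 80% to 100%.
- Final sample size: not given. SAP 12 says the interim analysis at 50% recruitment could not be carried out because the required number was not reached. Half of 148 is 74, so this implies at most 73 children, about 36 per arm. Values of 10, 20 and 36 per arm are used.

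**Relative risk built in by the design.** Suppose CPAP has no effect on clinical need. The recorded rates are still *q* and *c*, so the expected relative risk is about *q*/*c*:

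- 1.00/0.35 = 2.9
- 1.00/0.50 = 2.0
- 0.90/0.50 = 1.8
- 1.00/0.70 = 1.4

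**Two-sided Fisher p values.**

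| CPAP arm | Control arm | Relative risk | p |
|---|---|---|---|
| 36/36 | 13/36 | 2.8 | 1e-9 |
| 36/36 | 18/36 | 2.0 | 4e-7 |
| 32/36 | 13/36 | 2.5 | 6e-6 |
| 20/20 | 7/20 | 2.9 | 1e-5 |
| 18/20 | 10/20 | 1.8 | 0.014 |
| 16/20 | 10/20 | 1.6 | 0.096 |
| 10/10 | 5/10 | 2.0 | 0.03 |
| 9/10 | 4/10 | 2.3 | 0.057 |
| 10/10 | 7/10 | 1.4 | 0.21 |

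The direction is the same in every row. Significance depends on sample size, receipt and the control rate.

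**Separation.** If every CPAP-arm child has the event, the likelihood keeps rising as the treatment log odds ratio grows, and no finite maximum exists. In a check with 74/74 vs 37/74 and simulated covariates, the log odds ratio was 11.6, 21.6 and 31.6 after 10, 20 and 30 iterations, with standard errors of 23, 3,380 and 501,595. With a single non-receiver it settled at 4.46 (SE 1.05); the crude odds ratio is then (73/1)/(37/37) = 73.

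The chance of no non-receiver is *q*^n:

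- *q* = 95%: 0.95^36 = 16%; 0.95^20 = 36%.
- *q* = 90%: 0.90^36 = 2%; 0.90^20 = 12%.

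**The case against.** **Requirement could mean clinical need, not receipt.** On that reading, allocated CPAP would not count. It would even suit Protocol 3.0, where CPAP is given before it is needed to maintain gas exchange. But neither document states that definition or says how need would be judged in a child already on CPAP. For the primary outcome, the missing-data rule in SAP 7 treats requirement for Level 4 as receipt. If clinical need was intended, the SAP has to say so.

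**A reader might infer that the model is bound to separate and that Table 5e cannot be filled.** The documents do not support this. Analysis is by intention to treat (SAP 6), SAP 8.4 foresees incomplete CPAP delivery, and Table 2 has a row for children who received no CPAP. A child intubated directly under Protocol 10.6 and never given Level 2 or 3 would also not count. One such child makes the odds ratio finite, though no more interpretable.

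**A reader might also infer that the result will be highly significant whatever CPAP does.** This is not supported either. At 10 per arm, or with incomplete delivery and a high control rate, p can exceed 0.05, as the table shows.

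**Readers would not necessarily take the row as harm.** This is fair. Table 2 shows CPAP receipt by arm, and the documents openly describe CPAP as the allocated treatment. The misreading is possible, not inevitable.

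**It is one secondary outcome among several.** This stands, and it limits the severity.

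**Conclusion.** The point holds in a limited form. As written, the outcome is met by design by every child who receives the allocated CPAP, and by control children only through escalation. The Fisher test, relative risk and adjusted odds ratio therefore compare delivery of treatment with deterioration, and none of them estimates an effect on need for support. This conclusion follows from the text and needs no assumed rates.

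The size does rest on assumptions. With control rates of 35% to 50% and full receipt, the built-in relative risk is about 2 to 2.9, and at 20 to 36 per arm p is below 0.001. With less receipt, a higher control rate or 10 per arm, p ranges from 0.01 to above 0.2. Separation is a conditional risk, 16% at 36 per arm and 36% at 20 per arm if 95% receive Level 2/3, and the SAP names no fallback for it.

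This should be fixed. It does not touch the primary outcome or the mortality analyses.

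**What to change.** 1. In SAP 10.2, report receipt of Level 2 or Level 3 support by arm as numbers and percentages, with no p value and no model. SAP 8.3 covers CPAP only, so Level 3 must be added if the item moves there.
2. If a comparison is wanted, define it as escalation beyond the allocated CPAP: Level 3 or Level 4 within 30 days, defined the same way in both arms. The daily type-of-ventilation data (Protocol 11.4) support this.
3. Update SAP 3.3.2, the Table 4 row and Table 5e to match. Name a penalised (for example Firth) or exact method in case the model separates.
4. Declare the departure from Protocol 5.2.

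Counting Level 2/3 support only after the four-day intervention period is a weaker alternative. It drops early control escalations and is affected by earlier deaths.

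No new data are needed; the work is a paragraph, an outcome entry and two table edits. Two downsides must be stated. The SAP is dated 22/09/2016, after the planned end of recruitment in January 2016, so this is a late change to a protocol-named outcome in an open trial. Level 3 or 4 also contains the primary outcome, so the two will overlap. Descriptive reporting alone avoids the second.
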